#### TIME AND EVENTS TABLE

Study visit	1	2	3	4	5	6	7	8
	Days after the first vaccination							
Window (days)	0	( $\pm 1$ )	( $\pm 2$ )	( $\pm 2$ )	( $\pm 2$ )	( $\pm 3$ )	( $\pm 3$ )	( $\pm 10$ )
Study day	0	7	14	21	28	35	42	180
Informed consent	X							
Inclusion/exclusion criteria	X			X				
Medical/medication history	X							
Pregnancy test	X			X				
Blood sample – antibody studies	X	X	X	X	X	X	X	X
Vaccination	X			X				
Thermometer/Diary card	X			X				
Diary card training	X							
Diary card returned/review		X			X			
Reminder re unsolicited events	X	X	X	X	X	X	X	
Adverse events monitoring		X	X	X	X	X	X	X
Termination of study								X

Immunogenicity to influenza viruses will be evaluated by HI, MN, and possibly SRH responses.

#### 6.2 Planned duration of the study

Expected enrolment interval	Approximately 2 weeks
Duration of individual subject's participation	6 months
Total duration of study	Approximately 7 months
End of trial:	Corresponds to the last visit of the last subject undergoing the trial (LSLV)

Subjects will be screened and consented to ensure entry criteria are met and then vaccinated. After a second dose of vaccine on 21 days later, subjects will be followed-up for an additional 159 days.

#### 6.3 Premature discontinuation of the Study

The sponsor (UHL Trust), or the Chief Investigator (following consultation with the Department of Health/NIHR – the funder) has the right to discontinue this study at any time. If the clinical study is prematurely terminated, the Chief Investigator is to promptly inform the study subjects and should assure appropriate follow-up for the subjects. If the study is prematurely terminated, all procedures and requirements pertaining to archiving of documents will be observed.

#### **6.4 Discussion of overall study design**

This study was designed to evaluate immunogenicity of Baxter cell-culture, non-adjuvanted, whole virus H1N1 vaccine, and GSK AS03-adjuvanted, split H1N1 vaccine with respect to Committee of Human Medicinal Products (CHMP) and FDA licensing criteria, and occurrence of local and systemic symptoms and signs following vaccine administration in adult and elderly people who have never previously been vaccinated with pandemic H1N1 influenza vaccine. The exclusion criteria reduce the likelihood of prior pandemic H1N1 infection among vaccinees, but the timing of the study cannot avoid this possibility. Moreover it is possible that a further outbreak of pandemic H1N1 infection may occur during the first 42 days of the study. Nonetheless, this study design was considered best to evaluate the pandemic H1N1 vaccines purchased by the Government. The need for the study was discussed by advisors to the Department of Health. The study proposal was reviewed anonymously as part of the NIHR funding process.

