occur. Generally, cases have been limited to laboratory workers or those with occupational swine exposure. However, a pandemic alert was raised in 1976 when swine H1N1 caused an outbreak of respiratory illness with one fatality among 13 soldiers at a military base in Fort Dix, New Jersey, USA. No exposure to pigs was found and sero-epidemiological investigation identified up to 230 further soldiers had been infected suggesting human-to-human transmission. Mass vaccination of the US public was initiated and halted amid reports of adverse vaccine reactions, media scepticism and the lack of pandemic activity.

***Pandemic A/H1N1 emergence in 2009*** In April 2009, near the end of the usual influenza season in the Northern Hemisphere, the first two cases of swine origin H1N1 influenza virus were identified in the United States. The CDC confirmed that these cases were caused by a genetically similar swine virus that had not been previously identified in the United States. Genetic analysis of the strains showed that they were derived from a new reassortment of six gene segments from the known triple reassortant swine virus, and two gene segments (NA and matrix protein) from the Eurasian influenza A (H1N1) swine virus lineage. Effectively all isolates are susceptible to neuraminidase inhibitors, but resistant to M2 inhibitors. The World Health Organization raised its pandemic alert level to Level 6 on June 11 2009, reflecting community level outbreaks of novel H1N1 infection in at least two different WHO regions and the onset of a new pandemic. H1N1 virus has reached over 170 countries and territories worldwide as of August 6 2009, causing at least 177457 cases and 1462 deaths. In the UK, the first pandemic wave is waning, but a substantial increase in cases of novel H1N1 infection is expected following the re-opening of schools in September.

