**Visit 3: Day 14 ( $\pm 2$ ): Serology**

The following activities will be carried out on day 14 and recorded in the CRF:

1. Collect 10ml clotted blood for serology. Process blood and store serum.
2. Remind subject to notify study personnel immediately if the subject experiences a SAE.
3. Schedule the Day 21 visit.

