## **9.2 Statistical methods, sample size, and analyses**

### **9.2.1 Sample size**

The aim of the trial is to establish whether GSK and Baxter vaccines satisfy all three CPMP criteria, and if so compare them in terms of immunogenicity (for each vaccine/age group and each vaccine type). The sample size is in line with standard practice. The protocols for seasonal EU vaccine clinical trials and the criteria for assessment have been standardised within the EU. They stipulate that trials should be done with groups of at least 50 subjects. We will recruit 60 per group, allowing for up to 17% dropout. This will enable for example the trial to detect a 10% to 20% difference in seroprotection and seroconversion rates at the 5% significance level with 80% power.

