**9.2.5 Immunogenicity objectives**

**9.2.5.1 Primary immunogenicity objective**

The primary immunogenicity objective is to evaluate the immunogenicity of Baxter cell-culture, non-adjuvanted, whole virus H1N1 vaccine, and GSK AS03-adjuvanted, split H1N1 vaccine with respect to Committee of Human Medicinal Products (CHMP) and FDA licensing criteria.

These criteria for adults aged between 18 and 60 years are, for sera collected ‘approximately 3 weeks after vaccination’:

- Number of seroconversions or significant increase in antihaemagglutinin antibody titres >40%
- Mean geometric increase >2.5
- The proportion of subjects achieving an HI titre of  $\geq 40$  or SRH titre of  $25 \text{ mm}^2$  should be >70%

For adults aged over 60 years these criteria are:

- Number of seroconversions or significant increase in antihaemagglutinin antibody titres >30%
- Mean geometric increase >2.0
- The proportion of subjects achieving an HI titre of  $\geq 40$  or SRH titre of  $25 \text{ mm}^2$  should be >60%

The measures of immunogenicity will be calculated as:

*Geometric Mean Titre or Geometric Mean Area:* For each vaccine/age group and each vaccine type, least squares GMTs for HI and MN data (GMAs for SRH data), associated 95% confidence interval and median, minimal, and maximal titre value will be determined for each visit, i.e., days 0, 7, 14, 21, 28, 35, 42, and 180.

**Geometric Mean Ratio (increase):** For each vaccine/age group and each vaccine type, the least squares GMRs will be calculated for the HI, MN and SRH results for the following time points of the study: day 7/day 0, day 14/day 0, day 21/day 0, day 28/day 0, day 35/day 0, day 42/day 0, as well as the associated 95% confidence intervals and the median, minimal, and maximal n-fold increase. Statistical methods used to analyze GMRs will be identical to those described above for GMTs (GMAs).

**Seroconversions:** Percentages of subjects with seroconversion (or significant increase in HI titre). The number and proportion of subjects achieving seroconversion or significant increase in HI titres or SRH area from pre-immunization to each visit after first immunization will be tabulated for each vaccine/age group and each age group.

- Seroconversion is defined as negative pre-vaccination serum (<10 for HI, <4 for SRH) / positive post-vaccination titre ( $\geq 40$  for HI, area  $\geq 25 \text{ mm}^2$  for SRH).

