- Significant increase in antibody titre/area is defined as at least a fourfold increase in HI or a 50% increase in area from non-negative pre-vaccination serum ( $\geq 10$  for HI,  $\geq 4$  for SRH).

**Seroprotection:** Percentages of subjects achieving each of the following thresholds: inverse HI titre  $\geq 40$ , SRH area  $\geq 25 \text{ mm}^2$ : The number and proportion of subjects achieving each threshold at each visit will be tabulated for each vaccine/age group and each vaccine type.

All statistical analyses for HI and SRH will be performed on the logarithmically (base 10) transformed values. Titres below the limit of detection for assays will be set to 1 in 5 for HI and  $4 \text{ mm}^2$  for SRH for the purposes of analysis. Original values will be presented in all listings

The above immunogenicity criteria will be applied to sera collected 21 days after completion of vaccination, i.e., 21 days after the second vaccine dose. For pandemic vaccines, all three criteria should be met.

Should both GSK and Baxter vaccines satisfy all three CPMP criteria, we will compare the immunogenicity of the two vaccines (for each vaccine/age group and each vaccine type) in terms of:

- a. Geometric mean titres 21 days after each vaccination;
- b. Geometric mean ratio increases 21 days after each vaccination;
- c. Seroprotection rates 21 days after each vaccination;
- d. Seroconversion rates 21 days after each vaccination.

Comparisons will be made using parametric or non-parametric tests as appropriate for continuous outcomes, and Pearson's chi-square test or Fisher's exact test where appropriate for categorical outcomes. Further analyses using (generalised) linear models will explore the effect of baseline covariates on the outcomes. For populations (a) and (b), analyses using multiple imputation to allow for missing data will also be undertaken as a sensitivity analysis. No formal adjustment will be made for multiple testing but associated P-values will be interpreted cautiously.

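### Antibody rises from H1N1 infection after Day 0 count as vaccine response in the licensing verdicts, and no analysis shows whether a verdict depends on them

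*Protocol*

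**What the plan says.** **The hazard.** Section 4.0 reports that the first UK wave is waning but that "a substantial increase in cases of novel H1N1 infection is expected following the re-opening of schools in September". Section 6.5 plans the start for early September 2009. Section 6.4 says the exclusion criteria make prior infection less likely but cannot rule it out, and adds that "it is possible that a further outbreak of pandemic H1N1 infection may occur during the first 42 days of the study".

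**The verdict.** For ages 18 to 60, section 9.2.5.1 sets three limits: "Number of seroconversions or significant increase in antihaemagglutinin antibody titres >40" per cent, a mean geometric increase above 2.5, and seroprotection above 70%. For those over 60 the limits are 30%, 2.0 and 60%. On timing, "The above immunogenicity criteria will be applied to sera collected 21 days after completion of vaccination", which is Day 42. The one-dose verdict at Day 21 is part of the principal objective in the synopsis (Measures of Immunogenicity) but a secondary measure in 9.2.5.2(a).

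**Who is counted.** Section 6.7.5 includes in the immunogenicity assessment all who gave pre- and post-vaccination blood at the scheduled times. The per-protocol set in 9.2.2 requires correct dosing, evaluable sera and no major protocol violation. Infection is not named.

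**What is recorded after Day 0.** The Time and Events Table has adverse event monitoring at Visits 2-8 and marks the inclusion and exclusion criteria again at Visit 4. Sections 8.5 and 8.6 treat intercurrent illness as an adverse event, documented to three weeks after vaccination. Section 6.7.4 records prescriptions. Section 8.3 collects temperature, cough and coryza for seven days after each dose. Influenza-like illness as such is asked about only at Visit 1, for the period since May 2009. The Visit 2-7 step lists carry a safety reminder, "Remind subject to notify study personnel immediately if the subject experiences a SAE" (Day 14), or at Visit 4 its equivalent in the diary instructions. None has an influenza question.

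**The concern.** The criteria measure change from Day 0 within each vaccine group. A subject infected with the pandemic strain between Day 0 and the blood draw may show a fourfold rise and a titre of 40 or more whatever the vaccine did. Without an unvaccinated group the background rise cannot be subtracted. The error also has one direction: infection adds seroconverters, adds seroprotected subjects and raises the geometric mean increase, so all three criteria move towards a pass.

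At stake are the statement that a vaccine meets the licensing criteria at Day 42 and the statement that one dose suffices at Day 21. Section 9.2.7 sends the Day 0-21 and Day 21-42 antibody results to the Department of Health as interim information for vaccination strategy. A favourable verdict that rested partly on infection would go out with nothing to show it.

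**Working it through.** **The plan's own figure.** Section 9.2.1 says "We will recruit 60 per group, allowing for up to 17% dropout", and of the EU standards "They stipulate that trials should be done with groups of at least 50 subjects". 60 × (1 − 0.17) = 49.8, and 1 − 50/60 = 16.7%, so the group size reproduces to rounding (50/0.83 = 60.2). Both n = 60 and n = 50 are used below.

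**Inputs.** The limits come from 9.2.5.1 and the group sizes from 9.2.1. The true vaccine-only rate p and the infected share a are assumptions; the documents give neither.

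**Model.** Infection is independent of vaccine response and every infected subject responds before the blood draw. Then

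observed rate = p + a(1 − p).

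A criterion is passed when the observed proportion exceeds the limit. For >40% that is at least 25 of 60 or 21 of 50. For >70% it is at least 43 of 60 or 36 of 50. The probability is the exact binomial tail.

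*Seroconversion, limit >40%, p = 35%*

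| a | expected rate | pass, n = 60 | pass, n = 50 |
|---|---|---|---|
| 0 | 35.0% | 17.1% | 18.6% |
| 2% | 36.3% | 23.1% | 24.3% |
| 5% | 38.25% | 33.7% | 34.1% |
| 10% | 41.5% | 53.9% | 52.5% |

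*Seroprotection, limit >70%, p = 65%*

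| a | expected rate | pass, n = 60 | pass, n = 50 |
|---|---|---|---|
| 0 | 65.0% | 17.2% | 18.8% |
| 2% | 65.7% | 20.2% | 21.7% |
| 5% | 66.75% | 25.4% | 26.5% |
| 10% | 68.5% | 35.4% | 35.8% |

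The first row of each table is chance, because the criteria are judged on point estimates. Only the increase over that row is due to infection.

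**Break-even share.** The share that lifts the expected rate exactly to the limit L is a = (L − p)/(1 − p):

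- Seroconversion 40%: from 38%, 0.02/0.62 = 3.2%; from 35%, 0.05/0.65 = 7.7%.
- Seroprotection 70%: from 68%, 0.02/0.32 = 6.3%; from 65%, 0.05/0.35 = 14.3%.

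**Mean geometric increase.** With true increase g and an assumed fold rise F in infected subjects, a = ln(2.5/g)/ln(F/g). For g = 2.2 this gives 9.9% (F = 8), 6.4% (F = 16) and 4.8% (F = 32).

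**Does the text deal with it?** The supplementary analyses in 9.2.5.1 are covariate models and multiple imputation for missing data. Section 9.2.5.3 lists prior seasonal vaccination, age, baseline antibody and vaccine type as covariates, plus vaccination date if allocation is sequential. None uses infection after Day 0, and none changes either vaccine's comparison with the limits.

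**The case against.** **Infection is recorded.** A reader might infer from the visit lists that nothing about infection is captured after Day 0. The protocol does not support that. With doses on Days 0 and 21, three weeks of adverse event documentation after each covers Days 0-42, and intercurrent illness is included. Prescribed antivirals reach the concomitant medication form, the diary covers a week after each dose, and section 8.5 makes a vaccine failure that results in the disease a reportable serious event. The table's Day 21 check includes confirmed H1N1 and antiviral use, although the Visit 4 list omits that step. So the gap is a dated, influenza-specific prompt and a use for the data, not an absence of data.

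**The analysis plan may hold a rule.** It may, and major violations are to be defined before analysis. But the inclusion rule in 6.7.5 is in the protocol, infection is not a protocol deviation, and any later rule needs dated events that visits must collect.

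**Other stronger readings.** Section 6.4 calls an outbreak in the window possible; the stronger word, expected, is in section 4.0 and concerns national cases. Day 21 is not plainly a primary verdict, since section 9 makes it secondary. A reader might also extend the point to the comparison between vaccines. Under concurrent randomisation infection raises both arms and tends to shrink differences, and under sequential allocation 9.2.5.3 already acknowledges temporal bias and adds vaccination date as a covariate.

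**The size is hypothetical.** This stands. Late infections would add less, and all three criteria must be met, whereas the figures take one at a time.

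**Setting sera aside is itself biased.** This also stands. If 10% of vaccine non-responders, and no responders, were infected and removed, a true 35% would read 0.35/(0.35 + 0.65 × 0.9) = 0.35/0.935 = 37.4%. Removal on symptoms alone could also discard vaccine reactions, and unequally by vaccine.

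**Conclusion.** The point holds in this form: followed as written, the protocol counts infection-induced rises as vaccine response at Day 42 and Day 21, the effect runs only towards a pass, and nothing planned would show whether a verdict depends on it.

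How much this matters turns on an infection share the documents do not give. A vaccine 2 points below one of the adult rate limits needs about 3% to 6% infected to reach it in expectation; one 5 points below needs about 8% to 14%. A vaccine well clear of the limits is unaffected. These figures assume that all infected subjects respond in time and independently of vaccine response, and they are per criterion. They do not show that either vaccine would pass wrongly, and a vaccine just below a limit can pass one criterion by chance without any infection.

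**What to change.** 1. At Visits 2-7, add to the existing adverse event review one dated prompt, covering the time since the last visit, for laboratory-confirmed H1N1 and for antiviral treatment of influenza-like illness.
2. Reconcile the table, which marks the entry criteria at Day 21, with the Visit 4 list, which omits them. Also reconcile the standing of the Day 21 verdict between the synopsis and 9.2.5.2(a).
3. In 9.2.5.1 and 9.2.5.2(a), repeat each Day 42 and Day 21 verdict as a sensitivity analysis with sera taken after the onset of such an event set aside. Untreated, unconfirmed influenza-like symptoms should not trigger this, because they overlap with vaccine reactions.
4. Report the number of subjects affected by vaccine and age band, and state in the conclusion any verdict that changes.

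The cost is one form entry per visit and one repeat analysis, with no extra visit or assay. Silent infection is still missed, and setting sera aside conditions on an event after vaccination. The repeat verdict therefore stands beside the main one and does not replace it.

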#### **6.5 Start date**

The study is planned to commence early September 2009.

#### **6.6 Study setting**

This multicentre study will be conducted in University Hospitals of Leicester, Nottingham, and Sheffield, and possibly in GP surgeries in Leicestershire, Nottinghamshire, Yorkshire and Derbyshire.

#### **6.7 Study population**

##### **6.7.1 Initial approach**

We will approach staff and healthcare workers in university and healthcare settings in Leicester, Nottingham, and Sheffield either directly (i.e., personal contact), or through written information by post, email, or poster advertising. We may also request GPs to contact potentially suitable patients, either in writing or verbally, asking whether they would be prepared to learn more about the study with a view to participation. We may advertise the study through news items or advertisements on the local radio or in local newspapers. Respondents will be enrolled after they receive a detailed explanation of the study protocol and providing they meet inclusion and exclusion criteria and give signed informed consent. We will approach staff in frontline areas (acute admissions unit, acute wards, intensive care, bone marrow units) before non-health care workers are enrolled.

##### **6.7.2 Inclusion criteria:**

1. Mentally competent adults, who have signed an informed consent form after having received a detailed explanation of the study protocol.
2. Clinically healthy, male or female volunteers aged 18 years of age and older, including the over 65's, and those with **stable** high-risk medical conditions. (NOTE: 'Stable' is defined as having no medical consultations for an exacerbation or worsening of any chronic medical condition during the preceding 8 weeks, AND have been maintained on a stable drug regimen for at least 2 weeks prior to study entry as assessed by the medical history).
3. Are able to understand and comply with all study procedures and to complete study diaries,
4. Individuals who can be contacted and are available for all study visits.
5. Females should either be using secure contraceptive precautions including a) the oral contraceptive pill, b) condom/barrier contraception c) partner has had a vasectomy, d) be surgically sterilised, or e) post-menopausal (defined as at least two years since the last menstrual period).

### 6.7.3 Exclusion criteria:

- 1 Subjects who are unable to lead an independent life either physically or mentally;
- 2 Women should not be pregnant or lactating;
- 3 Women who refuse to use a reliable contraceptive method Days 0 to 42 of the study;
- 4 Confirmed H1N1 infection, as determined by laboratory tests;
- 5 Have received Oseltamivir or Zanamivir for influenza-like illness since May 2009;
- 6 Have a household member who had confirmed H1N1 infection, as determined by laboratory tests, and/or received Oseltamivir or Zanamivir for influenza-like illness since May 2009;
- 7 Receipt of another investigational agent (vaccine or medicinal product) in the preceding 4 weeks;
- 8 Unwilling to refuse participation in another study during Days 0 to 42 of the study;
- 9 Any clinically significant concurrent illness or unstable medical condition including: malignant tumours, acute or progressive renal or hepatic pathology, chronic obstructive pulmonary disease requiring oxygen therapy, and any active neurological disorder;
- 10 Individuals who have had acute respiratory pathology or infections requiring systemic antibiotic or antiviral therapy during the preceding 7 days (chronic antibiotic therapy for prevention of urinary tract infections is acceptable);
- 11 Subjects who had a temperature  $\geq 38^{\circ}\text{C}$  within 3 days of vaccination;
- 12 Any acute illness at the time of vaccination. Note: minor infections without fever or systemic upset are not contraindications/exclusion criteria;
- 13 Subjects with known or suspected impairment/alteration of immune function, including:
  - receipt of oral immunosuppressive drugs or other drugs listed in section 8 of the British National Formulary (BNF) or chloroquine, gold or penicillamine or other drugs listed in section 10.1.3 of the BNF to suppress a chronic disease process (Note: long-term, inhaled steroids for asthma management is acceptable),
  - receipt of immunostimulants or interferon,
  - receipt of an immunoglobulin preparation, blood products, and/or plasma derivatives within 3 months of the study;
  - Anyone at high risk of developing immunocompromising condition;
  - Received radiotherapy or chemotherapy during the 6 months preceding the study;
- 14 Subjects for whom surgery is planned during Days 0 to 42 of the study;
- 15 Regularly drink more than 40 units of alcohol weekly;
- 16 Known or suspected drug abuse (recreational or prescribed);
- 17 Individuals who, in the opinion of the investigator, have conditions that might complicate interpretation of the study results;
- 18 Subjects with a history of anaphylaxis or serious reactions to vaccines; known hypersensitivity (other than anaphylactic reaction) to influenza viral protein, to any

component of the study vaccines, to products containing mercury and to residues (egg and chicken protein, ovalbumin, formaldehyde, gentamicin sulphate, sodium deoxycholate, and benzonase).

- 19                               Subjects with a history of any neurological symptoms and signs, or anaphylactic shock following administration of any vaccine;
- 20                               Actual or planned receipt of another vaccine, excluding seasonal influenza vaccine, during the period 3 weeks before to 3 weeks after vaccination on Days 0 and 21.

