- 17 Individuals who, in the opinion of the investigator, have conditions that might complicate interpretation of the study results;
- 18 Subjects with a history of anaphylaxis or serious reactions to vaccines; known hypersensitivity (other than anaphylactic reaction) to influenza viral protein, to any component of the study vaccines, to products containing mercury and to residues (egg and chicken protein, ovalbumin, formaldehyde, gentamicin sulphate, sodium deoxycholate, and benzonase).
- 19 Subjects with a history of any neurological symptoms and signs, or anaphylactic shock following administration of any vaccine;
- 20 Actual or planned receipt of another vaccine, excluding seasonal influenza vaccine, during the period 3 weeks before to 3 weeks after vaccination on Days 0 and 21.

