## CONCOMITANT VACCINES/MEDICATIONS

There are no concomitant vaccines or medication.

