***Burden of H1N1 disease, hospitalisations and admissions to ITU*** As of August 7, analysis of the distribution by age of 8974 individual case reports of influenza A(H1N1)v infection in 27 EU/EEA countries reveal that the age-distribution of non-hospitalised cases of H1N1 influenza is highest in the 10-19 year age group, followed by 0-9 and 20-29 year age groups. The age-distribution of hospitalised cases is significantly higher in the 20-29 year age group than in the under 20's. Estimates of transmissibility ( $R_0$  1.4-1.6) are significantly higher than observed in seasonal influenza and comparable to previous pandemics. In England, admission rates have been highest in the under 5's, but life-threatening complications requiring admissions to ITU increase with age and presence of 'high-risk' co-morbidity. It is unclear whether the higher prevalence of infection in the under 30's is related primarily to social mixing, cross-reacting antibodies that are more prevalent with increasing age, or both.

Preliminary studies in the United States have shown that cross-reactive microneutralisation (MN) antibody titres of  $\geq 160$  to A/California/2009 H1N1 were detected in 6% of adults aged 18 to 40 years, 9% of adults 18 to 64 years, and 33% of adults aged 60 years and older. After vaccination with seasonal vaccine, 7% of adults aged 18 to 40 years, 25% of adults aged 18 to 64 years, and 43% of adults aged 60 years and older had post-vaccination titres of  $\geq 160$ .

Infection with the current influenza H1 pandemic virus is mostly mild, with no increase in mortality above threshold national statistics the United States, despite widespread infection. The observed age distribution is unusual and different from seasonal influenza, being skewed towards younger age groups, resulting in deaths and ITU admissions in people who are normally affected less frequently.

Currently it is difficult to be certain about the impact of novel H1N1 infection on hospitalisation rates. A rate of 11% has been observed in the United States, but this is likely to be an overestimate due to the mild nature of the disease in many cases, and differences in clinical practice. An overall rate for Europe is around 5%-6%, but this too may be an overestimate due to the practice in some countries of admitting patients for isolation to control spread, rather than for severity of illness. In the UK, the observed rate has been around 1-2%.

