#### **6.7.4     Prior and concomitant treatment**

During this trial medication prescribed to the subject prior to the start of the study will not be collected. All prescription medication (except minerals and vitamins), including non-study vaccines, being taken by the subjects on entry to the study and all prescription medication given in addition to the study vaccine during this clinical trial are to be regarded as concomitant medication and must be documented on the Concomitant Medications CRF.

In consideration of the overlapping Northern Hemisphere influenza vaccination campaign, the use of seasonal flu vaccines during the period 3 weeks before to 3 weeks after vaccination on Days 0 and 21 is an exclusion criterion.

All subjects may continue therapy for chronic medical conditions provided that they are not listed in section 8 of the British National Formulary (BNF) or include chloroquine, gold or penicillamine or other drugs listed in section 10.1.3 of the BNF to suppress a chronic disease process. Subjects with chronic medical conditions must be maintained on a stable regimen for at least 2 weeks prior to study entry as assessed by the medical history.

Use of other medication including over-the-counter products should be discouraged during the study. Investigational drugs are prohibited during the course of the study.

The following concomitant treatments are discouraged and, if used, might lead to a major protocol violation and result in withdrawal of the subject from the study according to the medical judgment of the lead physician (See exclusion criteria, 6.7.3; and Removal of subjects from therapy or assessments, 6.7.5):

- Systemic steroids,
- Other immunosuppressive agents,
- Blood or plasma derivatives, including immunoglobulin,
- Non-study vaccines (with the exception of post-exposure vaccinations in a medical emergency, e.g., hepatitis, rabies, tetanus) within 2 weeks.

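### Exclusion criterion 20 exempts seasonal influenza vaccine around the study doses, while section 6.7.4 calls its use in the same window an exclusion criterion

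*Protocol*

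**What the plan says.** Four statements in the protocol bear on seasonal influenza vaccine around the study doses.

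- Section 6.7.3, criterion 20, lists as an exclusion "Actual or planned receipt of another vaccine, excluding seasonal influenza vaccine, during the period 3 weeks before to 3 weeks after vaccination", counted around each of the two study doses. The synopsis criterion has the same carve-out: "Actual or planned receipt of another vaccine, excluding seasonal influenza vaccine".
- Section 6.7.4, referring to the overlapping seasonal campaign, states that "use of seasonal flu vaccines during the period 3 weeks before to 3 weeks after vaccination on Days 0 and 21 is an exclusion criterion".
- Section 6.7.4 also lists treatments that are discouraged and might amount to a major violation. One is "Non-study vaccines (with the exception of post-exposure vaccinations in a medical emergency, e.g., hepatitis, rabies, tetanus) within 2 weeks". Seasonal vaccine is not exempted there.
- The synopsis section on concomitant vaccines says: "There are no concomitant vaccines or medication".

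Section 4.0 gives the reason this matters. Before seasonal vaccine, cross-reactive MN titres of at least 160 to the pandemic strain "were detected in 6% of adults aged 18 to 40 years, 9% of adults 18 to 64 years, and 33% of adults aged" 60 and over. After it, the share was 7% at 18 to 40, and "25% of adults aged 18 to 64 years, and 43% of adults aged 60 years and older had post-vaccination titres of" at least 160.

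**The concern.** Criterion 20 and section 6.7.4 cover the same vaccine and the same window and give it opposite status. This is an eligibility rule that three centres must apply at enrolment and, by the time and events table, check again on Day 21. A subject given seasonal vaccine between the two doses is eligible under one section and excluded under the other.

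The disputed window holds the sera on which the licensing criteria are judged. A seasonal dose after Day 0 can add apparent responders. A dose before Day 0 can raise the baseline titre, which lowers the fold rise and makes seroconversion harder, while it may still help seroprotection. The direction of any distortion therefore depends on timing.

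There are two routes to a distorted result. Centres may apply different rules. Also, under scenario B of section 7.4, which the protocol calls the more likely one, the two vaccines are given one after the other, so a change in seasonal uptake over the autumn could fall unequally on the two arms.

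**Working it through.** **The texts side by side**

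| Place | Window | Status of seasonal vaccine |
|---|---|---|
| Synopsis and 6.7.3, criterion 20 | 3 weeks before to 3 weeks after Days 0 and 21 | Exempt from the exclusion |
| 6.7.4, seasonal campaign paragraph | The same | Exclusion criterion |
| 6.7.4, discouraged treatments | 2 weeks | Discouraged, possible major violation |
| Synopsis, concomitant vaccines | None stated | None foreseen |

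The first two rows cannot both be followed, and nothing in the protocol ranks one above the other.

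**The window.** From 21 days before Day 0 to 21 days after Day 21 is Day -21 to Day 42, or 63 days. Section 9.2.5.1 applies the licensing criteria 21 days after the second dose, which is Day 42. The Day 0 baseline and the Day 21 sera also fall inside.

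**Possible size.** The protocol states no figure for this effect, so there is none to reproduce. Inputs:

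- Shares with MN of at least 160 before and after seasonal vaccine, from section 4.0: 6% to 7% (18 to 40), 9% to 25% (18 to 64), 33% to 43% (60 and over). The rises are 1, 16 and 10 points.
- Seroprotection limits from 9.2.5.1: 70% up to age 60, 60% above.
- Assumption: the chance of newly crossing MN 160 carries over to HI 40.
- Assumption: uptake f in the window lies between 10% and 100%. The protocol gives no uptake.

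The chance that a subject below the threshold is lifted over it is x = (post - pre) / (1 - pre):

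- 18 to 64: 0.16 / 0.91 = 0.176
- 60 and over: 0.10 / 0.67 = 0.149
- 18 to 40: 0.01 / 0.94 = 0.011

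If t is the rate due to the study vaccine alone, the observed rate is t + (1 - t) × x × f. Setting this equal to a limit L gives t = (L - x f) / (1 - x f), the study-vaccine rate that would be lifted exactly to the limit.

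| Uptake f | t for L = 70%, 18 to 64 figures | Lift | t for L = 60%, 60 and over figures | Lift |
|---|---|---|---|---|
| 10% | 69.5% | 0.5 | 59.4% | 0.6 |
| 25% | 68.6% | 1.4 | 58.4% | 1.6 |
| 50% | 67.1% | 2.9 | 56.8% | 3.2 |
| 100% | 63.6% | 6.4 | 53.0% | 7.0 |

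On the 18 to 40 figures the lift is at most 0.3 points. With 60 × (1 - 0.17) = 49.8, or about 50 evaluable subjects per group, 7 points is 0.07 × 50 = 3.5 subjects.

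**The comparison of vaccines.** In the extreme case of 100% uptake in one arm and none in the other, with a true rate of 65% in both, the observed rates are 65% and 0.65 + 0.35 × 0.176 = 71.2%. A test at the 5% level then rejects with probability of about 10% with 50 per arm and about 21% with 150 per arm.

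**The case against.** The best counter-argument accepts the contradiction and disputes how much follows from it. Most of it stands.

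- A reader might set the 16- and 10-point rises beside the 10% to 20% difference in section 9.2.1 and conclude that seasonal vaccine could mimic the effect the trial is sized to detect. The documents do not support that. The rises are before-and-after changes in MN among people who all received seasonal vaccine; the sample-size figure is a between-arm difference in seroprotection or seroconversion. Also, 18 to 64 spans both younger strata, so the 16 points cannot be assigned to the 45 to 64 stratum.
- A reader might call seasonal vaccine uncontrolled in the primary endpoint. That is too strong. Section 6.7.4 sends non-study vaccines to the Concomitant Medications CRF; a major violation leaves the per-protocol set (9.2.2); previous seasonal vaccination and baseline antibody enter exploratory models; and under sequential allocation 9.2.5.3 acknowledges temporal bias and adds vaccination date as a covariate.
- A reader might take all 63 days as campaign time. The protocol gives no campaign dates, and with an early September start Day -21 falls in mid-August for the first subjects.
- The 2-week and 3-week texts are not a second direct contradiction. One is a list of discouraged treatments, the other an eligibility rule. They overlap and need aligning.
- Covariates, sensitivity analyses and the list of major violations may properly sit in a statistical analysis plan, so their absence here is no fault.

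The safeguards are nevertheless partial. Section 6.7.4 also says that medication prescribed before the study is not collected. Visit 1 asks about vaccination over three past seasons without asking for a date. Visits 2 and 5 review only the preceding week's medication, and Visits 3, 4, 6 and 7 list no question about vaccines. A dose shortly before Day 0 may thus go undated, and a violation cannot be defined coherently while the rule itself has two versions.

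**Conclusion.** The point holds as an internal contradiction in an eligibility rule. It needs correcting before the first subject is enrolled, because subjects admitted under different rules cannot be made comparable afterwards. That conclusion rests on the text alone and does not depend on any estimate of size.

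The numerical consequence is modest and uncertain: about 0.5 to 7 points of seroprotection near the 60% and 70% limits, and negligible on the 18 to 40 figures. It rests on two assumptions that the protocol does not supply, namely uptake and carry-over from MN to HI, and it covers only inflation of seroprotection. A dose before Day 0 could push fold rise and seroconversion the other way. A few points matter only where a group lies close to a limit.

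**What to change.** 1. Before enrolment, reconcile criterion 20 (synopsis and 6.7.3), both statements in 6.7.4 and the synopsis section on concomitant vaccines into one rule with one window. Which rule applies is for the sponsor to decide.
2. Whatever the rule, record the date of any seasonal influenza vaccine from Day -21 to Day 42 on the existing Concomitant Medications CRF, expressly including doses before Day 0.
3. State how such subjects are handled, in the protocol or the statistical analysis plan. If the rule permits seasonal vaccine in the window, repeat the primary analysis without them as a sensitivity analysis. If it does not, list it as a major violation for the per-protocol set.

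The cost is a wording correction, one dated entry on an existing form, and either one sensitivity analysis or one line in the list of violations. Sample size and visits do not change.
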